After the individual patient's end of the trial the Investigator does not need to actively monitor the patient for AEs but should only report relevant SAEs and relevant AESIs of which the Investigator may become aware of by any means of communication, e.g. phone call. Those AEs should be reported on the BI SAE form, but not on the CRF.

The rules for Adverse Event Reporting exemptions still apply, please see [Section 5.3.6.3.](#)

The REP is defined as 7 days after the last dose of trial medication is taken. All AEs which occurred through the treatment phase and throughout the REP will be considered as on treatment, please see [Section 7.3.4.](#) Events which occurred after the REP will be considered as post treatment events.

AE reporting to sponsor and timelines

The Investigator must report SAEs, AESIs, and non-serious AEs which are relevant for the reported SAE or AESI, on the BI SAE form via fax immediately (within 24 hours) to the sponsor's unique entry point (country specific contact details will be provided in the ISF). The same timeline applies if follow-up information becomes available. In specific occasions the Investigator could inform the sponsor upfront via telephone. This does not replace the requirement to complete and fax the BI SAE form.

With receipt of any further information to these events, a follow-up SAE form has to be provided. For follow-up information the same rules and timeline apply as for initial information.

Information required

For each AE, the Investigator should provide the information requested on the appropriate CRF pages and the BI SAE form. The Investigator should determine the causal relationship to the trial medication.

The following should also be recorded as an (S)AE in the CRF and SAE form (if applicable):

- Worsening of the underlying disease or of other pre-existing conditions
- Changes in vital signs, ECG, physical examination and laboratory test results, if they are judged clinically relevant by the Investigator.

If such abnormalities already pre-exist prior to trial inclusion they will be considered as baseline conditions.

All (S)AEs, including those persisting after an individual patient's end of trial must be followed up until they have resolved, have been sufficiently characterised, or no further information can be obtained.

Pregnancy

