7.3.4 Safety analyses

Adverse events will be coded using the Medical Dictionary for Drug Regulatory Activities (MedDRA) coding dictionary. Standard BI summary tables and listings will be produced. All adverse events with an onset between start of treatment and end of the residual effect period (REP), a period of 7 days after the last dose of trial medication, will be assigned to the treatment period for evaluation.

All treated patients will be included in the safety analysis. In general, safety analyses will be descriptive in nature and will be based on BI standards. No hypothesis testing is planned.

Statistical analysis and reporting of adverse events will concentrate on treatment-emergent adverse events (i.e., by 'treatment at onset'). To this end, all adverse events occurring between start of treatment and end of the residual effect period will be considered 'treatment-emergent'. Adverse events that start before first drug intake and deteriorate under treatment will also be considered as 'treatment-emergent'.

Frequency, severity, and causal relationship of adverse events will be tabulated by system organ class and preferred term after coding according to the current version of the Medical Dictionary for Drug Regulatory Activities (MedDRA).

Laboratory data will be analysed both quantitatively as well as qualitatively. The latter will be done via comparison of laboratory data to their reference ranges. Values outside the reference range as well as values defined as clinically relevant will be highlighted in the listings. Treatment groups will be compared descriptively with regard to distribution parameters as well as with regard to frequency and percentage of patients with abnormal values or clinically relevant abnormal values.

Vital signs, physical examinations, or other safety-relevant data observed at screening, baseline, during the course of the trial and at the end-of-trial evaluation will be assessed with regard to possible changes compared to findings before start of treatment.

Descriptive statistics are planned to quantify the frequency of patients with suicidal ideation and behaviour as recorded on the C-SSRS at any post-baseline visit.

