3. INTRODUCTION

As per ICH E9, the purpose of this document is to provide a more technical and detailed elaboration of the principal features of the analysis described in the protocol, and to include detailed procedures for executing the statistical analysis of the primary and secondary variables and other data.

This TSAP assumes familiarity with the Clinical Trial Protocol (CTP), including Protocol Amendments. In particular, the TSAP is based on the planned analysis specification as written in CTP Section 7 “Statistical Methods and Determination of Sample Size”. Therefore, TSAP readers may consult the CTP for more background information on the study, e.g., on study objectives, study design and population, treatments, definition of measurements and variables, planning of sample size, randomization.

SAS® Version 9.4 or higher will be used for all analyses.

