4. CHANGES IN THE PLANNED ANALYSIS OF THE STUDY

Due to recruitment challenges, the trial has a much smaller sample size than originally intended. The following are the changes in the analyses due to the limited sample size:

- No subgroup analyses.
- No evaluation of psychometric properties of SIPS/SOPS.
- No additional sensitivity analyses excluding patients who were recruited from the enriched population prior to amendment 3.

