7.8 SAFETY ANALYSIS

All safety analyses will be performed on the treated set. Analyses are specified in **section 7.3.4** of the CTP.

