7.8.1 Adverse events

Unless otherwise specified, the analyses of adverse events will be descriptive in nature. All analyses of AEs will be based on the number of subjects with AEs and NOT on the number of AEs.

The analysis of adverse events will be based on the concept of treatment emergent adverse events. That means all adverse events with an onset between start of treatment and end of the on-treatment period, which is 7 days after the last dose of trial medication, will be assigned to the treatment period for evaluation. All adverse events occurring before first drug intake will be assigned to 'screening' and all adverse events occurring after the residual effect period will be assigned to 'post-treatment' (for listings only).

According to ICH E3 (5), AEs classified as 'other significant' need to be reported and will include those non-serious and non-significant adverse events with:

- (i) 'action taken = discontinuation' or 'action taken = reduced', or
- (ii) marked haematological and other lab abnormalities or lead to significant concomitant therapy as identified by the Clinical Monitor/Investigator at a Medical Quality Review Meeting.

An overall summary of adverse events will be presented. The frequency of subjects with adverse events, and will be summarized by treatment, primary system organ class and

preferred term. Separate tables will be provided for subjects with other significant adverse events according to ICH E3 (5), for subjects with adverse events of special interest (only if defined) and for subjects with serious adverse events.

The system organ classes and preferred terms (within system organ class) will be sorted by frequency.

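### SAP 7.8.1 drops the protocol rule that adverse events starting before first dose and worsening on treatment are treatment-emergent, so the safety tables may omit some subjects

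*SAP*

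**What the plan says.** Protocol section 7.3.4 gives two routes by which an adverse event becomes treatment-emergent. The first is by onset: events that begin between the start of treatment and the end of the residual effect period, "a period of 7 days after the last dose of trial medication, will be assigned to the treatment period for evaluation". The second is by worsening: "Adverse events that start before first drug intake and deteriorate under treatment will also be considered as" treatment-emergent.

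SAP section 7.8.1 adopts the treatment-emergent concept and then explains it by the first route only: "all adverse events with an onset between start of treatment and end of the on-treatment period", again ending 7 days after the last dose. It continues: "All adverse events occurring before first drug intake will be assigned to" screening. Events after the residual effect period go to a post-treatment category used for listings only. The section says nothing about worsening.

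Three other statements bear on how this should be read:

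- SAP section 7.8 says of the safety analyses: "Analyses are specified in section 7.3.4 of the CTP".
- SAP section 3 says that "the TSAP is based on the planned analysis specification as written in CTP Section 7".
- SAP section 4 introduces its departures from the protocol with "The following are the changes in the analyses due to the limited sample size" and lists three: no subgroup analyses, no psychometric evaluation of SIPS/SOPS, and no sensitivity analysis excluding the enriched patients recruited before amendment 3. None concerns adverse events.

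**The concern.** The SAP is the document from which the tables will be programmed, and section 7.8.1 reads as a complete allocation rule: before first dose, on treatment, after. A programmer who follows it as written would place in screening an event that the protocol places on treatment. The SAP does not record this as a decision, so a reader of the trial report could not tell whether the protocol definition or a narrower one had been used.

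The events at issue can occur. Protocol section 5.3.6.2 has adverse events collected from signed consent, and the flow chart places screening 28 to 7 days before dosing, so every patient has a period in which an event can begin before the first tablet. SAP 7.8.1 counts subjects rather than events. A subject whose only event in a table row began in that period and worsened under its original onset date would therefore be absent from the row. The rule is the same in both arms, but if the drug itself worsens such events, more of the omitted subjects would be on active treatment. That is the signal the deterioration rule is there to catch.

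**Working it through.** No arithmetic applies: neither document states a figure for these events, and the point rests on a classification rule. The check is to run the possible cases through both texts.

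| Case | Protocol 7.3.4 | SAP 7.8.1 read literally |
|---|---|---|
| A. Onset from first dose to last dose + 7 days | Treatment-emergent | Treatment-emergent |
| B. Onset between consent and first dose, never worsens | Not treatment-emergent | Screening |
| C. Onset between consent and first dose, worsens on treatment, worsening entered as a new record with an on-treatment onset | Treatment-emergent | Treatment-emergent |
| D. As C, but worsening kept on the old record with its original onset date | Treatment-emergent | Screening |
| E. Condition already present before consent, worsens on treatment, recorded as an adverse event with an on-treatment onset | Treatment-emergent | Treatment-emergent |

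The texts disagree only in case D. How often it arises depends on three things.

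1. **Recording practice.** Protocol section 5.3.6.2 requires this to be recorded as an adverse event: "Worsening of the underlying disease or of other pre-existing conditions". That settles case E. It does not say whether worsening of an event first reported during screening opens a new record (case C) or changes the intensity on the old one (case D). If every worsening became a new on-treatment event, the deterioration sentence in protocol 7.3.4 would have nothing to do. Its presence suggests that case D was expected at least sometimes.

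2. **Which text governs.** SAP 7.8 points to protocol 7.3.4, where case D is treatment-emergent; SAP 7.8.1 sends case D to screening. The SAP is thus inconsistent with itself, and section 4 gives no decision to resolve it.

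3. **Other events in the same row.** Because subjects are counted once, a case D subject with another on-treatment event in that row is counted under either rule.

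The range is therefore logical, not numerical. The lower end is zero: worsening is always entered as a new record, or the programmer applies protocol 7.3.4. The upper end is the number of case D subjects with no other qualifying event in the row. The documents give no input from which to calculate it.

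**The case against.** The strongest reply is that SAP 7.8.1 is an incomplete restatement, not a contrary rule. Its onset sentence closely follows the protocol's own, SAP 7.8 refers to the protocol section that holds the deterioration rule, SAP section 3 bases the plan on protocol section 7, and section 4 announces no change. The protocol also relies on the sponsor's standard tables, and the SAP cites a sponsor standard on adverse event data that is not available here. All of this is fair. It shows that the protocol rule may well be applied in practice. It does not remove the contrary sentence in 7.8.1, which is the more specific text and has no exception.

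A reader might infer that the tables will undercount on-treatment harm. The documents do not support that as a flat statement, because worsening may be recorded as a new event with an on-treatment onset, which SAP 7.8.1 would count.

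A reader might also infer that the gap is wide because these patients have psychiatric symptoms at entry. That does not follow either. Symptoms present before consent are not events with onset in screening, and their worsening is recordable in its own right. Serious suicidal ideation and suicidal behaviour after baseline must be reported as separate serious events (protocol section 5.3.6.1). Psychosis is handled as an outcome event, with serious event reporting only where a causal link to study drug is suggested (protocol section 5.3.6.3). The affected pool is limited to events that first begin between consent and first dose.

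Finally, the safety analysis is descriptive and without hypothesis tests, so no formal conclusion turns on this. That limits the weight of the point but does not excuse two definitions of the main safety population of events.

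**Conclusion.** The point holds as a conflict between documents with a conditional consequence. SAP 7.8.1 is narrower than protocol 7.3.4, the narrowing is not declared, and the reference in SAP 7.8 leaves the SAP inconsistent rather than curing it. Subjects may be omitted from the safety tables if three conditions are met: their event began between consent and first dose, it worsened on treatment, and the worsening stayed under the original onset date. They must also have no other qualifying event in the same row.

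The size cannot be derived and may be zero. It is tempting to multiply assumed rates of screening events and of worsening by the planned 300 patients. Neither rate is in the documents, and SAP section 4 says that the trial is much smaller than intended, so no such figure is offered. The correction is worth making because it is cheap and decides which definition the reported tables use.

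**What to change.** Amend SAP 7.8.1 so that events with onset before first dose that deteriorate between first dose and last dose + 7 days are treatment-emergent, and all other pre-dose events are assigned to screening. Add how worsening is dated and recorded: as a new record, or as a dated change of intensity on the existing one. Without this, the restored rule could count the same worsening twice, once through the old record and once through a new one. If the sponsor prefers the narrower rule, it should be declared and justified in SAP section 4.

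The same edit should reconcile the residual effect period, since the rule depends on where the treatment period ends. SAP section 6.1 calls it 28 days; protocol sections 5.3.6.2 and 7.3.4 make it 7. Under the 28-day reading, SAP 7.8.1 leaves events on days 8 to 28 after the last dose in neither the on-treatment nor the post-treatment category.

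The cost of the main change is one or two SAP sentences and a small derivation. No new assessment or visit is needed. The documents do not say whether the case report form captures dated changes of intensity, so this should be confirmed before the derivation is written.

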7.8.2 Laboratory data

The analyses of laboratory data will be descriptive in nature and will be based on BI standards (6). Planned analyses are detailed in **section 7.3.4** of the CTP.

Baseline for safety laboratory parameters will be the last available measurement before the start of randomized treatment. Laboratory measurements taken up to 7 days after the last administration of randomized treatment will be considered as on-treatment.

[figure not shown]
Only patients with at least one available on-treatment value will be included in the analysis of an individual laboratory parameter. All individual data will be presented in listings. If there are multiple safety laboratory values at one visit, the worst of these will be assigned to that visit date measurement.

7.8.3 Vital signs

Only descriptive statistics are planned for this section of the report. See **section 7.3.4** of the CTP.

[figure not shown]
7.8.4 ECG

12-lead ECG measurements will be assessed as described in the CTP Flow Chart. ECG findings before first intake of study drug will be considered as baseline condition. Any clinically significant new findings in the ECG measurement after the first ECG will be considered as AE and analyzed as planned in [section 7.8.1](#).

10. HISTORY TABLE

Table 10: 1 History table

Version	Date (DD-MMM-YY)	Author	Sections changed	Brief description of change
Initial	13-DEC-17		None	This is the initial TSAP with necessary information for trial conduct
Final	21-MAY-21		All were updated.	This is the final TSAP
